Cabozantinib is a small molecule inhibitor of the tyrosine kinases c-Met and VEGFR2, and has been shown to reduce tumor growth, metastasis, and angiogenesis. Its role has been clearly established in well differentiated thyroid cancer however it has not been evaluated in SCCHN. Given the recent approval of pembrolizumab for platinum failing patients with RM disease, a combination trial of cabozantinib with pembrolizumab is a rational approach in this patient population.

OBJECTIVES

The objectives of this study are:

Primary Objectives:

Run in phase: To determine the safety and tolerability of pembrolizumab and cabozantinib in patients with recurrent and/or metastatic SCCHN

Phase II: To estimate the overall response rate (ORR) of patients with RM SCCHN who receive the combination of pembrolizumab and cabozantinib

Secondary Objectives:

- To estimate the progression free survival of patients treated with the combination of pembrolizumab and cabozantinib

- To further define the toxicities associated with these regimens in patients with SCCHN.

Exploratory Objectives:

- To identify potential biomarkers related to response to combination of pembrolizumab and cabozantinib in patients with recurrent and/or metastatic HNSCC.
 - Evaluate whether markers of angiogenesis, hypoxia, Met or pMet expression, or inflammatory activation can predict response to the combination or PFS.
 - Evaluate circulating cell free DNA (cfDNA) in plasma and its association with response to the combination or PFS.
 - Evaluate potential neoantigens in the tumor DNA, their expression, and their association with response to the combination or PFS.
 - Evaluate peripheral blood mononuclear cells (PBMC) for immune monitoring and their association with response to the combination or PFS.
- To determine a quantitative radiomics based on CT and/or PET images as a prognostic biomarker in recurrent or metastatic HNSCC.
- To determine a computational pathology (or pathomics) based prognostic marker from standard digitized H&E images of the tumor in recurrent or metastatic HNSCC.

STUDY DESIGN

Run in phase:

Pembrolizumab will be initiated in Cycle 1 at the standard dose of 200 mg Q 3 weeks.

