There may be possible cooperative effects between pembrolizumab and cabozantinib based on cabozantinib's role in supporting a more immune permissive environment. It was recently shown that a suppressive tumor microenvironment plays a major role in the immunosuppression observed in patients with SCCHN; this is now better corroborated through biomarker studies suggesting that an inflamed T cell phenotype in the microenvironment contributed to a higher response to single agent pembrolizumab (Abstract #6009, ASCO 2017). Since cabozantinib produces a more immune permissive environment (Cabozantinib IB version 13, section 4.2.2), its combination with a checkpoint inhibitor such as pembrolizumab is welcomed.

In this protocol we will be starting with a cabozantinib dose of 40 mg daily instead of 60 mg daily, which is the dose approved for renal cell carcinoma. The rationale is based on unpublished information obtained from investigators indicating a poor tolerance to the combination of high dose cabozantinib at 60 mg with PD-1 inhibitors.

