2.2 Study Design

2.2.1 Overview of Study Design

All patients will require measurable disease by RECIST 1.1 and will need documentation of disease progression after platinum based therapy; archival tissue will need to be submitted; if archival tissue is not possible a fresh biopsy is mandated.

Run-in phase:

Pembrolizumab will be initiated in Cycle 1 at the standard dose of 200 mg Q 3 weeks for one cycle.

A run in phase of cabozantinib at 40 mg/day will be performed for the first 6 patients, beginning in Cycle 1. If the combination is well tolerated (<2 DLTs in the first cycle), the trial will complete accrual at this dose level. If the combination is not well tolerated, with 2 DLTs in the first treatment cycle observed in the first 6 patients, the dose of cabozantinib will be decreased to 20 mg/day which will be the dose used for the rest of the study.

DLT Criteria

Adverse events (AEs) will be graded in accordance to the National Cancer Institute Common Terminology Criteria for Adverse Events (CTCAE) (v4.0). Dose-limiting toxicity (DLT) is defined as any of the following treatment-related AEs occurring during the DLT Evaluation Period, which will be during the first cycle of combined pembrolizumab and cabozantinib.

- Treatment-Related Non-Hematologic AEs:
 1. Any related \geq Grade 3 AE which is unexpected in severity and/or duration compared to the known safety profiles of cabozantinib and pembrolizumab when used as single agents, and that cannot be managed by dose modification (reduction or interruption) and adequate supportive care, and requires permanent discontinuation of cabozantinib and/or pembrolizumab.

2. Inability to take $\geq 75\%$ of the total planned cabozantinib dose for the DLT Evaluation Period because of a treatment-related AE leading to dose reductions and/or interruptions

For the AEs described in Section 3.3.2 - 3.3.2.19, the specific AE management guidelines in this section should be followed to determine the need for dose reductions and dose interruption.

- Treatment-Related Hematologic AEs:
 1. Grade 3 neutropenia of ≥ 7 days duration or any Grade 4 neutropenia
 2. \geq Grade 3 febrile neutropenia;
 3. All other hematologic toxicities of Grade 4 (except anemia as described in Section 3.3.2.4)

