A subject will be replaced if the subject does not have a DLT but is not fully evaluable for DLT due missing more than 25% in total of the dosing days due to progressive disease or for reasons other than cabozantinib-related toxicity.

Each subject's course will consist of three periods:

- A Pre-Treatment Period in which subjects are consented and undergo screening assessments to be qualified for the study (Section 16.o);
- A Treatment Period in which subjects receive study treatment and undergo study assessments (Section 16.o);
- A Post-Treatment Period in which subjects no longer receive study treatment but undergo follow-up study assessments and contacts (Section 16.o).

Phase II:

Pembrolizumab will be administered at the standard dose of 200 mg Q 3 weeks. Cabozantinib will be given at the dose determined in the run in phase. Both agents will be initiated on Day 1 of Cycle 1 and will continue in combination for the rest of the study.

Patients will be evaluated every 3 weeks on the study with a physical exam, clinic visit. CT scans MRIs or PET/CT will be required for staging every 9 weeks.

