2.7 Withdrawals

Subjects may discontinue study treatment or withdraw their consent to participate in the study at any time without prejudice. The investigator may withdraw a subject from study treatment or from the study if, in his or her clinical judgment, it is in the best interest of the subject or if the subject cannot comply with the protocol.

In addition, any of the following conditions require discontinuation of the subject from study treatment:

- An AE or intercurrent illness that in the opinion of the investigator warrants the subject's withdrawal from study treatment;
- The investigator believes it is not in the best interest of the subject to continue on study
- Specific conditions described in the Management of Adverse Events Sections 3.3.2 and 3.3.2.1;
- Necessity for treatment with other anticancer treatment prohibited by protocol;
- Sexually active subjects who refuse to use medically accepted barrier methods of contraception (eg, male condom, female condom) during the course of the study and for 4 months after discontinuation of study treatment;
- Women who become pregnant or are breastfeeding;
- If the subject does not recover from his or her toxicities to tolerable Grade ≤ 2 within 6 weeks, the subject will have study treatment discontinued unless there is unequivocal evidence that the subject is benefitting. In this situation, a subject may be able to restart therapy with a dose reduction upon resolution of the toxicity and with agreement of the principal investigator / Sponsor;
- Request by regulatory agencies for termination of treatment of an individual subject or all subjects under the protocol;
- Significant noncompliance with the protocol schedule in the opinion of the investigator;
- The minimum dose of study treatment will be 20 mg once daily (qd). Subjects who cannot tolerate 20 mg qd will have study treatment discontinued;

- Progressive disease (PD) or the subject no longer experiences clinical benefit as determined by the investigator

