- Requires inpatient hospitalization or results in prolongation of an existing hospitalization;
- Results in persistent or significant disability or incapacity:
 - Note: The term “disability” refers to events that result in a substantial disruption of a subject’s ability to conduct normal life function.
- Is a congenital anomaly or birth defect;
- Is an important medical event (IME):
 - Note: The term “important medical event” refers to an event that, based upon appropriate medical judgment, may not be immediately life-threatening or result in death or hospitalization, but may jeopardize the subject or require intervention to prevent one of the other serious outcomes listed under the definition of SAE. Examples of IMEs include intensive treatment in an emergency room or at home for allergic bronchospasm; blood dyscrasias, or convulsions that do not result in hospitalization; or development of product dependency or product abuse.

▪ Serious Adverse Event Reporting

As soon as an investigator becomes aware of an AE that meets the definition of ‘serious,’ this should be documented to the extent that information is available.

- Investigator shall notify sponsor within twenty-four (24) hours of making such discovery by submitting a completed SAE report form and any other pertinent SAE information as indicated on the SAE reporting form;
- Written IND safety reports will be submitted to the FDA by the IND sponsor, for serious, unexpected suspected adverse reactions within 15 calendar days of learning of its occurrence. If the event is fatal or is deemed to be life threatening, the report will be made within 7 calendar days. The IND sponsor will also make an assessment of whether the event constitutes an unanticipated problem posing risks to subjects or others (UP). This assessment will be provided to the Emory University IRB, which, in turn will make

a final determination. If the Emory IRB determines an event is a UP it will notify the appropriate regulatory agencies and institutional officials.

- For multicenter studies the Investigator must notify the IND/CTA Sponsor by submitting a completed SAE report form and any other pertinent SAE information as indicated on the SAE reporting form within 24 hours to allow the IND/CTA Sponsor to submit the SAE report form to Exelixis no later than 2 business days.
- This report must be submitted by sponsor to Exelixis at e-mail: [contact] or [contact], even if it is not felt to be drug related;

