The DSMC will review pertinent aspects of the study to assess subject safety, compliance with the protocol, data collection, and risk-benefit ratio. Specifically, the Winship Cancer Institute Internal Monitors assigned to the DSMC may verify informed consent, eligibility, data entry, accuracy and availability of source documents, AEs/SAEs, and essential regulatory documents. Following the monitoring review, monitors will provide a preliminary report of monitoring findings to the PI and other pertinent individuals involved in the conduct of the study. The PI is required to address and respond to all the deficiencies noted in the preliminary report. Prior to the completion of the final summary report, monitors will discuss the preliminary report responses with the PI and other team members (when appropriate). A final monitoring summary report will then be prepared by the monitor. Final DSMC review will include the final monitoring summary report with corresponding PI response, submitted CAPA (when applicable), PI Summary statement, and available aggregate toxicity and safety data.

The DSMC will render a recommendation and rating based on the overall trial conduct. The PI is responsible for ensuring that instances of egregious data insufficiencies are reported to the IRB. Continuing Review submissions will include the DSMC recommendation letter. Should any revisions be made to the protocol-specific monitoring plan after initial DSMC approval, the PI will be responsible for notifying the DSMC of such changes. The Committee reserves the right to conduct additional audits if necessary.

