24. CONDITIONS FOR TERMINATING THE STUDY

Exelixis reserves the right to terminate the study, and investigators reserve the right to terminate their participation in the study, at any time. Should this be necessary, Exelixis and the investigator will arrange the procedures on an individual study basis after review and

consultation. In terminating the study, Exelixis and the investigator will ensure that adequate consideration is given to the protection of the subjects' interests.

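### If 40 mg/day fails the run-in, the trial moves to 20 mg/day with no DLT threshold at that dose; a short rule reusing the existing criteria would close the gap cheaply

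*Combined protocol and SAP*

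**What the plan says.** The synopsis (Study Design) and section 2.2.1 describe a run-in of six patients on pembrolizumab plus cabozantinib 40 mg/day. Section 2.2.1 treats fewer than two DLTs in cycle 1 as tolerable, and accrual then finishes at 40 mg/day. Otherwise, "the dose of cabozantinib will be decreased to 20 mg/day which will be the dose used for the rest of the study". For Phase II the same section says: "Cabozantinib will be given at the dose determined in the run in phase".

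The synopsis gives the run-in its own primary objective: "To determine the safety and tolerability of pembrolizumab and cabozantinib in patients with recurrent and/or metastatic SCCHN". Section 2.1 differs. It lists ORR as the only primary objective and puts toxicity among the secondary ones.

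Safety oversight continues whatever the dose:

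- Section 2.7 makes 20 mg once daily the minimum dose and adds: "Subjects who cannot tolerate 20 mg qd will have study treatment discontinued".
- Section 17, on serious adverse events: "Investigator shall notify sponsor within twenty-four (24) hours of making such discovery".
- Section 21: "The DSMC will review pertinent aspects of the study to assess subject safety". Its reviews occur every 6 months or annually, depending on the risk level.
- Section 26 has the sponsor report toxicity to the DSMC, and weekly teleconferences with the participating site cover toxicities.
- Section 24: "Exelixis reserves the right to terminate the study".

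None of these attaches a DLT number to a decision at 20 mg/day.

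**The concern.** The only decision tied to a DLT count is made once, at 40 mg/day. If that dose is rejected, the replacement becomes the Phase II dose without facing the same test. The DLT definition in section 2.2.1 is not tied to a dose, so DLTs could be recorded at 20 mg/day, but no number of them leads to any action.

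On that branch, the run-in would have applied its criterion only to the dose it rejected. Most of the trial's patients would receive a dose supported by descriptive adverse-event data and general oversight. It is also the lowest permitted dose. A patient who starts at 40 mg/day has one reduction available (Table 3-2); a patient who starts at 20 mg/day has none, and intolerance means stopping.

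**Working it through.** The plan gives no operating characteristics for the run-in, so there is no figure of its own to reproduce. The check applies its stated rule to assumed DLT rates. The documents give no DLT rate for the combination at either dose.

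**Inputs.** Six patients, with failure at two or more cycle-1 DLTs (section 2.2.1); up to 34 evaluable subjects, an interim look after 20 patients and accrual over 2 years (section 18); 21-day cycles (study assessments table).

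**Formula.** With true DLT rate p, P(fail) = 1 − (1−p)^6 − 6p(1−p)^5.

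| Assumed p | (1−p)^6 | 6p(1−p)^5 | P(2 or more of 6) |
|---|---|---|---|
| 0.05 | 0.7351 | 0.2321 | 0.0328 |
| 0.10 | 0.5314 | 0.3543 | 0.1143 |
| 0.20 | 0.2621 | 0.3932 | 0.3446 |
| 1/3 | 0.0878 | 0.2634 | 0.6488 |

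**Chance of reaching the 20 mg branch.** Taking p as the rate at 40 mg/day: 11%, 34% or 65% at 10%, 20% or 33%.

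**Patients affected.** 34 − 6 = 28, or 82% of 34. If the interim look stops the trial, 20 − 6 = 14, or 70% of 20. These are approximate. Two DLTs could occur before six patients have been treated, and the 34 counts evaluable rather than treated subjects.

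**What the same rule would do at 20 mg/day.** Under the current text the chance that a prespecified DLT rule triggers at 20 mg/day is zero at every rate. With the rule:

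- False pause at an acceptable rate: 3.3% at p = 0.05 and 11.4% at p = 0.10.
- Miss at p = 0.20: 1 − 0.3446 = 0.6554, about 66%.

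**Chance that 40 mg/day fails and the 20 mg/day check then pauses accrual.** The two cohorts are different patients, so at fixed rates the probabilities multiply:

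- 10% at 40 mg, 5% at 20 mg: 0.1143 × 0.0328 = 0.0037 (0.4%)
- 20% at 40 mg, 10% at 20 mg: 0.3446 × 0.1143 = 0.0394 (3.9%)
- 33% at 40 mg, 20% at 20 mg: 0.6488 × 0.3446 = 0.2236 (22%)

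**Pace of existing review.** At 34 patients over 2 years, 34/4 = 8.5 start in six months and 34/2 = 17 in a year, so roughly 8 to 17 could start between DSMC reviews. Serious adverse event reports and the weekly calls are quicker, but neither names a DLT count that forces a decision.

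**The case against.** The strongest reply is that this is a reasonable simple design. There is one step down, to half the failed dose and a third of the 60 mg for which section 1.3 reports "poor tolerance to the combination of high dose cabozantinib at 60 mg with PD-1 inhibitors". A lower DLT rate at 20 mg/day is plausible. With no lower dose available, a pause could lead only to continuing, amending or stopping, and existing oversight can already decide any of these. This stands, and it limits the value of the rule to supplying a defined trigger.

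A second reply is that a cycle-1 check shows little. Section 3.3.2 says most subjects need 2 to 3 weeks to reach cabozantinib steady state, so a 21-day window lies largely before it. Section 3.4.1 gives median onsets of 1.6 to 3.4 months for colitis and 1.7 to 4.3 months for pneumonitis on pembrolizumab, from other tumor types. This also stands, although the 40 mg/day run-in has the same limit and the plan accepts it there.

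Third, the synopsis (Number of Subjects) puts 6-9 patients in the run-in, which might suggest an extra cohort at 20 mg/day. The documents do not support that. The range carries no dose, threshold or action; the statistical text says 6; and the extra patients may simply be the replacements that section 2.2.1 allows.

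A reader might also infer that patients at 20 mg/day would go unmonitored, or that 20 mg/day is likely to be poorly tolerated. Neither follows. The oversight is real and can stop the trial, and the documents contain no DLT data for the combination at 20 mg/day.

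**Conclusion.** The gap is real but conditional. If 40 mg/day fails, 20 mg/day becomes the Phase II dose for about 28 of 34 patients without being held to the run-in's own criterion. If 40 mg/day passes, the gap does not arise. Adding the check is a worthwhile, inexpensive improvement; its absence does not leave the trial without safety control.

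The size depends entirely on assumed DLT rates. Across the three scenarios, the added rule would be both reached and triggered in 0.4% to 22% of trials, and the upper figure needs rates of 33% at 40 mg and 20% at 20 mg. The rule offers the same limited assurance as the existing six-patient test and no more. The argument from the run-in's objective also has limited weight, because safety is primary in the synopsis but toxicity is secondary in section 2.1.

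The differing run-in sizes, the fixed 40 mg starting-dose text in sections 3.2 and 3.3, and the re-escalation rule in section 3.3.1.1 are separate matters. This conclusion does not rest on them.

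**What to change.** Add to section 2.2.1 and the synopsis:

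> If the dose is decreased to 20 mg/day, the same cycle-1 DLT criteria apply to the first 6 DLT-evaluable patients started at 20 mg/day, drawn from the planned 34. Because no lower dose exists, non-hematologic criterion 1 is read as not manageable by interruption and supportive care. As soon as 2 of these patients have a DLT, accrual pauses for a sponsor and DSMC decision.

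The second sentence is needed because criterion 1 currently refers to management by dose reduction or interruption, and no reduction is possible from 20 mg/day.

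The change is protocol wording only and adds no planned patients. It imposes no enrolment hold unless two DLTs occur. The consequence is that a further patient may start while the sixth is still under observation: at planned accrual, 34/730.5 × 21 = 0.98, or about one. The cost, on this branch only, is the 3% to 11% false-pause risk shown above. A pause calls for a decision and does not stop the trial automatically.

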1.2.3.2.3 Deaths

As of 29 February 2016, the incidence of Grade 5 AEs from the pooled single-agent studies was 10.5% (254 subjects). The Grade 5 events that occurred at the highest frequency ($\geq 1\%$ incidence) were prostate cancer (2.9%) and general physical health deterioration (1.0%). Since prostate cancer was the progression of cancer in CRPC studies, only general physical health deterioration was assessed as related to study treatment. Thirty-three (33) of the 254 subjects with Grade 5 AEs had events assessed as related to the study treatment. The only related Grade 5

AEs that occurred more than once were pulmonary embolism (n=4), death (unspecified; n=3), hemorrhage (n=2), respiratory failure (n=2), and sudden death (n=2).

Further details can be found in the Investigator's Brochure,

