3.3.2.9 Thromboembolic Events

Thromboembolic complications are frequent in cancer patients due to procoagulant changes induced by the malignancy or anticancer therapy including inhibitors of VEGF pathways. Deep vein thrombosis and PE have been observed in clinical studies with cabozantinib; including fatal events (please refer to the Investigator's Brochure). Subjects who develop a PE or DVT should have cabozantinib treatment held until therapeutic anticoagulation with heparins (eg, low molecular weight heparin [LMWH]) is established. LMWH are the preferred management for thrombotic events, warfarin is not recommended. Cabozantinib treatment may be resumed in subjects who are stable and have uncomplicated PE or DVT and are deriving clinical benefit from cabozantinib treatment and that anticoagulation does not place them at a significant risk that outweighs the benefit of resuming treatment per discretion of the investigator/Sponsor. During anticoagulation treatment, subjects need to be monitored on an ongoing basis for bleeding risk and signs of bleeding which may require additional or more frequent laboratory tests in accordance to institutional guidelines. If there are any signs of clinically significant bleedings, cabozantinib treatment should be permanently discontinued.

Arterial thrombotic events (eg, transient ischemic attack, myocardial infarction) have been observed in studies with cabozantinib. Subjects should be evaluated for preexisting risk factors for arterial thrombotic events such as diabetes mellitus, hyperlipidemia, hypertension, coronary artery disease, history of tobacco use, and cardiac or thromboembolic events that occurred before initiation of study treatment. Cabozantinib treatment should be discontinued in subjects who develop an acute myocardial infarction, cerebral infarction or any other clinically relevant arterial thromboembolic complication.

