- Pulmonary toxicity: Immune-mediated pneumonitis has been observed, including fatal cases. For patients with melanoma, the median time to development was 4.3 months (range: ~2 days to ~19 months) and the median duration was 2.6 months (range: 2 days to ~15 months). Some patients required initial management with high-dose systemic corticosteroids, the median duration of initial corticosteroid therapy was 8 days (range: 1 to 34 days) followed by a corticosteroid taper. Pneumonitis completely resolved in nearly two-thirds of melanoma patients. For patients with NSCLC, the median time to development was 1.7 months (range: 4 days to ~13 months) and the median duration was 1.2 months (range: 5 days to ~12 months). Some NSCLC patients had complete resolution of pneumonitis. May require treatment interruption, corticosteroid therapy (prednisone 1 to 2 mg/kg /day [or equivalent] followed by a taper, for grade 2 or higher pneumonitis), and/or permanent discontinuation. Monitor for signs and symptoms of pneumonitis; if pneumonitis is suspected, evaluate with radiographic imaging and administer systemic corticosteroids for grade 2 or higher pneumonitis. For NSCLC, pneumonitis occurred more frequently in patients with a history of asthma, COPD, or prior thoracic radiation.

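### DLT item 1 applies its expectedness test to Grade 5 events too, so a related non-hematologic death of a known type late in cycle 1 can literally be scored as no DLT (very small effect, one-sentence fix)

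*Combined protocol and SAP*

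**What the plan says.** Section 2.2.1 (DLT Criteria) gives two non-hematologic routes to a DLT in the first cycle.

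- **Item 1** takes related events of Grade 3 or higher and joins three conditions with *and*. The event must be one "which is unexpected in severity and/or duration compared to the known safety profiles of cabozantinib and pembrolizumab when used as single agents"; it must not be manageable by dose modification and supportive care; and it must require permanent discontinuation of one or both drugs.
- **Item 2** counts a patient who could not take at least 75% of the planned cabozantinib "because of a treatment-related AE leading to dose reductions and/or interruptions".

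The hematologic items include febrile neutropenia of Grade 3 or higher, which covers Grade 5.

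The dose rule is: "If the combination is well tolerated (<2 DLTs in the first cycle), the trial will complete accrual at this dose level". With 2 DLTs in the first 6 patients, cabozantinib drops to 20 mg. On replacement: "A subject will be replaced if the subject does not have a DLT but is not fully evaluable for DLT", where not evaluable means that more than 25% of dosing days were missed.

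The safety profiles that item 1 refers to already contain deaths:

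- Section 1.2.3.2.3: "Thirty-three (33) of the 254 subjects with Grade 5 AEs had events assessed as related to the study treatment". Among the related ones, the only Grade 5 "AEs that occurred more than once were pulmonary embolism (n=4), death (unspecified; n=3), hemorrhage (n=2"), respiratory failure (2) and sudden death (2).
- Section 3.3.2.9: "Deep vein thrombosis and PE have been observed in clinical studies with cabozantinib; including fatal events".
- Section 3.4.1, pembrolizumab warnings: "Immune-mediated pneumonitis has been observed, including fatal cases".

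**The concern.** An expectedness filter is reasonable for non-fatal toxicity in a combination run-in, where the question is whether the pair is worse than its parts. Applied to deaths, it lets the classification turn on whether the investigator regards a fatal event of a known type as unexpected. Two people could read the same case differently, and the text supports either.

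The count of fewer than 2 DLTs in 6 sets the dose for the rest of the study, up to 34 − 6 = 28 further patients. If a related death occurs alongside exactly one other DLT, its label alone decides between 40 mg and 20 mg.

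**Working it through.** **1. Source rates.** The pooled single-agent cabozantinib data cover 2410 subjects (section 1.2.3.2). The stated Grade 5 incidence reproduces: 254/2410 = 10.54%, given as 10.5%. Related Grade 5: 33/2410 = 1.37%. Related deaths of types seen more than once: 4 + 3 + 2 + 2 + 2 = 13, and 13/2410 = 0.54%. By named type, pulmonary embolism is 4/2410 = 0.17% and hemorrhage 2/2410 = 0.08%. No rate is given for the combination, and none for fatal pneumonitis.

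**2. When item 2 stops helping.** A cycle is 21 days (study assessments table), and 0.75 × 21 = 15.75 daily doses. Fifteen full doses are 71.4%, so item 2 could apply. Sixteen are 76.2%, so it does not. The gap runs from just after the day-16 dose through day 21. Because item 2 is measured in total planned dose, any earlier hold or dose reduction shortens the gap, and a 5-day hold closes it.

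**3. Replacement.** A patient who dies after 16 doses has missed at most 5/21 = 23.8% of dosing days. This is below the 25% threshold, so the patient stays among the six without a DLT.

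**4. Chance of such a death in the run-in.** Assumptions: the single-agent rate p applies; it is spread evenly over K = 2, 4 or 8 cycles and over the days of a cycle; the window is w = 5 days, with no hold. Then

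P(at least one in 6) = 1 − [1 − (p/K)(w/21)]^6

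| Rate p | K = 2 | K = 4 | K = 8 |
|---|---|---|---|
| 33/2410 | 0.97% | 0.49% | 0.24% |
| 13/2410 | 0.38% | 0.19% | 0.10% |

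**5. What the label changes, given one such death.** Let X be the DLTs among the other five patients. If the death is not counted, the run-in passes when X ≤ 1. If it is counted, it passes only when X = 0. The difference is P(X = 1).

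| DLT rate in the others (assumed) | Pass, not counted | Pass, counted | Difference |
|---|---|---|---|
| 10% | 91.9% | 59.0% | 32.8 points |
| 20% | 73.7% | 32.8% | 41.0 points |
| 30% | 52.8% | 16.8% | 36.0 points |

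**6. Effect before the run-in starts.** Multiply step 4 by P(X = 1), in percentage points:

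- 13/2410: lowest 0.0963% × 0.328 = 0.03 (K = 8, rate 10%); highest 0.385% × 0.410 = 0.16 (K = 2, rate 20%).
- 33/2410: lowest 0.244% × 0.328 = 0.08; highest 0.974% × 0.410 = 0.40.

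An exact binomial over all six patients at a 20% DLT rate with 33/2410 agrees. Run-in passage is 0.65616 against 0.65216 at K = 2, a difference of 0.40 points.

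**7. Sensitivity to the window.** A 2-day hold (w = 3) cuts the 33/2410 range to 0.05–0.24. Counting the whole of day 16 as a sixth day multiplies the results by about 6/5, which takes the two maxima to about 0.19 and 0.48. Neither changes the order of magnitude.

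**The case against.** The best defense is the wording itself. Item 1 asks whether the event is unexpected in severity against the profile, not whether a fatal case has ever been reported. Related deaths were 1.4% over whole treatment courses. A death within three weeks at 40 mg, below the 60 mg approved in renal cell carcinoma (section 1.3), could readily be called unexpected, and it meets the other two conditions of item 1. This stands as a reason to expect most such deaths to be counted. The figures above apply no discount for it, so they lean high. It does not remove the gap, because the text permits the opposite answer.

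Other points also stand. Many fatal toxicities would first pass through holds: Table 3-3 requires immediate interruption at Grade 4, and section 3.3.2.9 holds cabozantinib for embolism. Median pneumonitis onset was 4.3 months in melanoma and 1.7 months in lung cancer, although the ranges start at days. The exclusion criteria screen out several bleeding risks.

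A reader might infer that the plan excludes deaths from the DLT count, or that any related death in cycle 1 escapes it. The documents do not support that: item 2 can catch earlier deaths, febrile neutropenia is covered at Grade 5, and item 1 admits any death judged unexpected. A reader might also infer that such a death would go unseen. It would not. There is 24-hour serious adverse event reporting, toxicity reporting to the data and safety monitoring committee, weekly calls with the participating site, and authority to terminate. What these provisions leave open is how the death enters the count of DLTs.

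**Conclusion.** The concern holds as a narrow defect of wording. A related non-hematologic death of a known type, after at least 16 full cabozantinib doses in cycle 1, can be scored as no DLT on a literal reading, and nothing in the protocol settles the matter otherwise.

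The average effect is very small. The 13/2410 range fits the concern better, since it is confined to recurring types; the 33/2410 range is the upper case. Both borrow a single-agent, whole-course rate for cycle 1 of a combination, so they indicate scale and do not predict. The conditional effect in step 5 is large, but only for an event with a chance of about 1% or less among the six patients under these assumptions. Nothing here touches the response-rate endpoint, its sample size or its error rates. This is worth considering because the remedy is nearly free, not because the risk is large.

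**What to change.** Add one sentence to the DLT Criteria in section 2.2.1: *Any treatment-related Grade 5 event during the DLT Evaluation Period is a DLT, regardless of expectedness or the number of doses taken.* Leave the criteria for non-fatal events unchanged, so that the expectedness filter keeps its purpose there.

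The change needs no extra patients or procedures. Its downside mirrors its effect: the chance of stepping down to 20 mg rises by the same small amount, and only when a related death occurs together with exactly one other DLT among six patients, where the lower dose is the cautious choice.
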